2.4.2. Justification for the primary study objective

It is possible that prolonged endocrine therapy has a positive effect on the rate of recurrence.

2.4.3. Therapy plan

In the ATAC study, anastrozole was administered in the therapy plan for 5 years, thus this duration of therapy constitutes a sensible rationale. Since a portion of the patients who are to be included in the protocol had already been treated with anastrozole for 3 years (ABCSG-8), these patients will also receive the aromatase inhibitor in the 2-year group of the present study for a total of 5 years. The difference between 2 and 5 years is clinically relevant (see the discussion of tamoxifen 2 decades ago) and mathematically realistic.

3. OBJECTIVE

3.1. Primary objective

- 3.1.1. Assessment of the effect in terms of disease-free survival (DFS) of a further 2 years of anastrozole vs. a further 5 years of anastrozole after 5 years of adjuvant endocrine therapy

3.2. Secondary objective

- 3.2.1. Assessment of the effect in terms of overall survival (OS) of a further 2 years of anastrozole vs. a further 5 years of anastrozole after 5 years of adjuvant endocrine therapy
- 3.2.2. Comparison of the fracture rate between the two treatment groups
- 3.2.3. Comparison of the occurrence of secondary cancers between the two treatment groups
 - 3.2.3.1. Comparison of the occurrence of contralateral breast cancer between the two treatment groups
 - 3.2.3.2. Comparison of the occurrence of secondary cancers, with the exception of a contralateral breast cancer, between the two treatment groups

4. DESIGN

This is a prospective, randomised, open-label, multicentre phase III study in HR-positive breast cancer patients in the adjuvant setting.

All patients who are relapse-free at 60 months after surgery will be randomised after 5 years of primary endocrine treatment and maximum break in therapy of 12 months (e.g. from Studies 8 and 9 of the ABCSG) to:

- Arm A: 2 years of therapy with anastrozole (Arimidex®)
- Arm B: 5 years of therapy with anastrozole (Arimidex®)

The treatment phase lasts for 2 or 5 years. The follow-up phase has been set at 8 years in Arm A and 5 years in Arm B.

Planned study start:	December 2003
Planned recruitment end:	December 2008
Planned end of the maximum treatment phase:	December 2013
Planned end of follow-up:	December 2018

5. STUDY POPULATION

5.1. Sample size

The aim is to recruit 3500 patients in a multicentre design.
Full details of the statistical calculation of sample size can be found under item 10.

5.2. Inclusion criteria

1. Postmenopausal patients with histologically verified invasive or minimally invasive breast cancer that has been radically treated locally with or without previous chemotherapy and/or radiotherapy
2. Age \leq 80 years
3. No distant metastasis at randomisation
4. No recurrence at randomisation
5. TNM-classification at the time of diagnosis: T1-3, N0-1, M0
6. Oestrogen and/or progesterone receptor-positive before the start of primary endocrine therapy
7. Endocrine therapy for 5 years (maximum deviation \pm 12 months)
8. Therapy break (from the preliminary therapy) maximum 12 months
9. At the time of randomisation, the results of the following tests must be available:
 - a) Medical history and clinical examination (within one month prior to randomisation)
 - b) Gynaecological examination (within one month prior to randomisation)
 - c) Chest x-ray or CT scan (within one year prior to randomisation)
 - d) Bilateral mammogram (within one year prior to randomisation) – exception are women with mastectomy (unilateral)
 - f) Ultrasound of the abdomen or abdominal CT (within one year prior to randomisation)
 - e) Laboratory parameters (within 3 months prior to randomisation)
 - Adequate liver function (GOT or GPT \leq 2.5 x ULN; total bilirubin $<$ 2 x ULN, AP $<$ 2 x ULN)
 - Serum creatinine \leq 1.5 x ULN
10. Informed consent prior to randomisation

5.3. Exclusion criteria

1. Premenopausal patients or patients with non-determinable menopausal status at randomisation
2. Manifest secondary malignancy or status post secondary malignancy between the time of initial diagnosis and randomisation
3. General contraindications and/or hypersensitivity to anastrozole
4. Carcinoma in situ of any size with or without Paget's disease of the nipple or T4 tumours at the time of initial diagnosis
5. Receptor determination unknown or negative at the time of diagnosis or at the start of the primary endocrine therapy
6. Age $>$ 80 years
7. Performance index $>$ 3 as per WHO
8. Regular use of hormone products and hormone replacement therapy (HRT) for more than 6 months since the primary breast cancer surgery
9. Serious concomitant disease preventing implementation of adjuvant therapy in line with the protocol and/or controlled follow-up
10. Lack of patient cooperation

11. Legal incapacity and/or other circumstances preventing the patient from understanding the nature, significance and implications of the clinical trial
12. Existing psychiatric disease as per ICD at study enrolment (especially alcohol dependency)

5.4. Premature termination of the clinical study

5.4.1. Premature termination in an individual case

Reasons leading to study discontinuation are:

1. Withdrawal of patient consent
2. Occurrence of intolerable adverse events
3. Occurrence of relapse, secondary cancer or death of the patient
4. Lack of compliance or cooperation of the patient
5. Serious protocol violation
6. Other personal reasons for the patient (e.g. change of location); there is usually the possibility of ongoing care at another ABCSG study site
7. Patient no longer attends (lost to follow-up): the maximum time frame for this is
 - In the therapy phase: +6 months calculated from the scheduled visit date (see 6.5.)
 - In the follow-up phase: +12 months from the scheduled visit date

The investigator must make every effort to establish contact with the patient.

Each patient has the right to withdraw their consent to take further part in the clinical trial at any time and without giving reasons. You will not be disadvantaged as a result. The investigator will attempt to ascertain the reasons for the discontinuation, but the patient's rights must not be violated. The time of the discontinuation, the results to date, and, if known, the reason for the patient's discontinuation should be documented in the patient file and the CRF. If a patient wishes to withdraw from the study, they must be asked whether or not they agree to the further use of their clinical data (in particular to disease-related events and follow-up) for study-related purposes.

The investigator may also terminate the trial if he no longer deems the patient's participation to be justified e.g. from a medical point of view. The date and reason for discontinuation, as well as all observations gathered up to the point of discontinuation are to be recorded in the medical history and CRF.

The investigator will continue to observe patients who were removed from the study due to intolerable adverse events until these have resolved or findings have normalised.

All patients, regardless of whether the treatment was discontinued prematurely or not, will receive follow-up care as per the study protocol. Data will be collected and documented in accordance with the FUP guidelines (see 7.3.).

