1.2. Flow chart

Parameter	Screening	6 months	12 months	24 months	36 months	48 months	60 months	6 years	7 years	8 years	9 years	10 years
Verification of inclusion and exclusion criteria	X											
Medical history	X											
Clinical examination	X	X	X	X	X	X	X	X	X	X	X	X
Gynaecological examination	X		X	X	X	X	X					
Ultrasound or CT of abdomen	X		X	X	X	X	X					
Chest x-ray or CT	X		X	X	X	X	X					
Bilateral or unilateral mammogram	X		X	X	X	X	X	X	X	X	X	X
Measurement of bone density (optional)	X		X	X	X****	X****	X****					
Survey of fracture rate		X	X	X	X	X	X					
LFP*	X		X	X	X	X	X					
RFP**	X		X	X	X	X	X					
TU marker*** (optional)	X		X	X	X	X	X					
SAE/AE												
				See point 9							See point 9	

Legend: * LFP: GOT,GPT, AP, total bilirubin

** RFP: Serum creatinine

*** TU marker: CEA, CA 15-3

**** Only for patients in Arm B (5 years of anastrozole)

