7.2.3. After 36, 48 and 60 months (Arm B)

1. Clinical examination
2. Survey of fracture rate
3. Adverse events leading to discontinuation of therapy
4. Serious adverse events
5. Laboratory parameters:
 - LFP (GOT, GPT, total bilirubin, AP)
 - RFP (serum creatinine)
 - Optional TU marker: CEA, CA 15-3
6. Gynaecological examination
7. Radiological examinations
 - Sonography of the abdomen or abdominal CT
 - Chest x-ray or CT
 - Bilateral mammogram (unilateral mammogram in the case of mastectomy)
 - Bone density measurement (optional)

The time frame for these examinations is defined as +/- 6 months. If the patient does not attend the visit at the designated interval, this results in the patient being set to the off position.

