7.2.2. After 12, 24, 36, 48 and 60 months

1. Physical examination
2. Survey of fracture rate
3. Adverse events leading to discontinuation of therapy
4. Serious adverse events
5. Development of hepatic, renal insufficiency
6. Optional TU marker: CEA, CA 15-3
7. Gynaecological examination
8. Radiological examinations
 - Sonography of the abdomen or abdominal CT
 - Chest x-ray or CT
 - Bilateral mammogram (unilateral mammogram in the case of mastectomy)
9. Bone density measurement (optional)

Affected protocol point:

- 7. Implementation
- 7.3. Follow-up (page 28)

Old text:

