7.3. Follow-up

After the therapy is complete, follow-up examinations are carried out at 36, 48 and 60 months in Arm A analogously to the therapy examinations in the Arm B. After the 60th monthly visits, the standardised follow-up examinations are carried out at yearly intervals (+/- 6 months) over a period of 5 years for both arms.

1. Physical examination
2. Bilateral mammogram (unilateral mammogram in the case of mastectomy)
3. Serious adverse events (see 9.1 and 9.2.4)

Affected protocol point:

- 1.2. Flow chart (page 12)

Old text:

1. Separate specification for patient history and clinical examination
2. No detailed information for gynaecological examination

Amended text:

1. Change to physical examination
2. Gynaecological examination with asterisk * in screening: * Including ultrasound (exception: status post hysterectomy) or ** at the therapy visits: ** "Follow-up examination in accordance with the current state of scientific knowledge"

Justification for the amendment:

- Points 9a–9f in the inclusion criteria are handled in a separate point (i.e. Amendment in point 1 "Patient selection" or additional point 5.4 "Diagnosis") (reason: The above-mentioned examinations from point 9 are not actual inclusion criteria but rather constitute guidelines for how inclusion criteria 3 and 4 are should be ensured.)
- Change of description in the exclusion criteria: "Manifest secondary malignancy or status post secondary malignancy between the time of initial diagnosis and randomisation" to "manifest secondary malignancy or status post secondary malignancy" (reason: misleading description; there are patients who were included status post secondary cancer who had to be set to ineligible.)
- The gynaecological examination at screening has been supplemented by a mandatory ultrasound examination (reason: accurate clarification of any pathological changes which otherwise could be attributed to the study medication is possible at inclusion.)
- The time frame for the gynaecological examination is extended to 6 months (reason: it is not feasible to obtain findings in a time frame of one month prior to randomisation.)

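### The protocol routes early stoppers to section 7.3, which sets the 36-, 48- and 60-month examinations for Arm A only and conflicts with 7.2.2, so outcome ascertainment in years 2 to 5 may differ by arm

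*Protocol*

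**What the plan says.** - **Who is followed.** Protocol 5.4.1, renumbered 5.5.1 by Amendment 1, keeps early stoppers in follow-up: "All patients, regardless of whether the treatment was discontinued prematurely or not, will receive follow-up care as per the study protocol". It then names the schedule: "Data will be collected and documented in accordance with the FUP guidelines (see 7.3". The amendment shows no change to either sentence.
- **Section 7.3 as amended.** For months 36 to 60: "follow-up examinations are carried out at 36, 48 and 60 months in Arm A analogously to the therapy examinations in the Arm B". The lighter phase begins later: "After the 60th monthly visits, the standardised follow-up examinations are carried out at yearly intervals", for both arms. The itemised list is physical examination, mammogram and serious adverse events. It has no fracture survey and no chest or abdominal imaging.
- **Section 7.2.2 as amended.** The heading is "7.2.2. After 12, 24, 36, 48 and 60 months". The list includes the fracture survey, the gynaecological examination and chest and abdominal imaging. It states no arm and no treatment status.
- **Section 7.2.3 of the main protocol.** Headed "7.2.3. After 36, 48 and 60 months (Arm B"), it sets the same kind of visit by month. Amendment 1 does not expressly delete it.
- **Flow chart of the main protocol.** Only bone density at months 36 to 60 is arm-specific: "Only for patients in Arm B (5 years of anastrozole").
- **SAP.** The main DFS analysis starts 2 years after randomisation (3.5.2). Time to first fracture also starts at 2 years, and fracture-free women are censored at their last therapy visit, at most about 5 years after randomisation (3.6.4).

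**The concern.** Planned treatment in Arm A ends at 2 years, so early stopping between years 2 and 5 can occur only in Arm B. A woman in Arm A who is off drug at year 3 has the full examinations written for her in 7.3. A woman in Arm B who stopped at 2.5 years is sent to the same section and finds no schedule for herself until after month 60. A site could give her the full visits under 7.2.2, or could apply only the items itemised in 7.3.

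Under the second choice, asymptomatic distant relapses in these women could be found later and some non-serious fractures could be missed. Both would fall on Arm B alone, inside the main DFS window and across the whole fracture window. Both would tend to make 5 years look better, in an open-label trial where sites know the arm.

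**Working it through.** The plan gives no figure on this point, so the check is mainly a comparison of texts.

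**Step 1: follow each woman through the text, months 36 to 60.**

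| Woman | Via 5.4.1 to amended 7.3 | Via amended 7.2.2 |
|---|---|---|
| Arm A, off drug (planned or early) | Full examinations, matched to Arm B | Full examinations |
| Arm B, on drug | Not in 7.3 | Full examinations |
| Arm B, stopped early | Nothing stated before month 60 | Full examinations |

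Only the third row depends on which route is taken. Section 7.3 does not put her on the reduced list before month 60. It gives her no schedule at all.

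**Step 2: would a DFS analysis show the difference?** SAP 3.5.2 accepts any treatment or follow-up visit with a cancer status evaluation and states no imaging requirement. A visit without imaging therefore counts as event-free.

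**Step 3: fracture censoring.** Arm A is past its planned treatment from year 2, when the fracture clock starts. If a therapy visit meant a visit on drug, Arm A would have almost no fracture follow-up. The term must therefore include visits off drug, at least in Arm A. For Arm B early stoppers it is undefined. If they stay at risk without a survey, fractures can be missed. If they are censored on stopping, they leave the risk set because of a treatment-related event after randomisation.

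**Step 4: illustrative size.** The documents give no stopping rate by arm and no detection rate, so everything here is assumed. Let f be the share of Arm B events in years 2 to 5 that arise in women off drug, and m the share of those events missed.

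Apparent HR (A versus B) = true HR / (1 − f × m)

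As a guide to f: if a proportion s of Arm B stops evenly over 5 years, the off-drug share of person-time in years 2 to 5 is s × 3.5/5 = 0.7s. For s of 20% to 40% that is 14% to 28%. The wider range of 10% to 40% is used for f.

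For DFS, m = 5% to 30%; 1.35 is the planned hazard ratio.

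| f | m | True HR 1.00 appears as | True HR 1.35 appears as |
|---|---|---|---|
| 10% | 5% | 1/0.995 = 1.005 | 1.35/0.995 = 1.36 |
| 20% | 20% | 1/0.96 = 1.04 | 1.35/0.96 = 1.41 |
| 40% | 30% | 1/0.88 = 1.14 | 1.35/0.88 = 1.53 |
| any | 0 (7.2.2 applied to all) | 1.00 | 1.35 |

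The formula treats a late-detected relapse as lost, so it overstates the effect on an analysis that uses all follow-up. For fractures the extreme case is m = 1 with stoppers kept at risk: 10% to 40% of Arm B fractures in the window would be missed.

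**The case against.** The strongest reply is that the full schedule already runs by time since randomisation. Amended 7.2.2 has no arm or drug condition, 7.2.3 of the main protocol sets the Arm B visits by month, and the main flow chart limits only bone density to Arm B. Amended 7.3 names Arm A in order to match it to Arm B, so its evident aim is equal ascertainment. The sentence in 5.4.1 covers all patients and is not a special rule for early stoppers. Amendment 2 says the flow chart will be adjusted to Amendment 1; the adjusted chart is not in the text available here and might settle the matter.

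Much of this stands, and it rules out stronger readings.

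- A reader might infer that Arm B early stoppers are placed on the reduced list before month 60, so that ascertainment does differ by arm. No passage says so.
- A reader might infer that non-serious fractures reach the database only through the survey. Protocol 9.1 excepts fractures from the rule that non-serious events stay out of the CRF, and 10.5 speaks of fracture rates during or after treatment. The survey is the scheduled prompt, not the only route.
- A reader might take 1 minus the 14% to 28% share as a null fracture ratio (B/A) of 0.72 to 0.86. That needs stoppers kept at risk with no fracture captured. SAP 3.6.4 may instead censor them.
- A reader might multiply the same share by an assumed 25% to 50% of relapses found only by imaging and quote a 4% to 14% understatement of the Arm B DFS hazard. DFS also counts deaths, contralateral cancers and second cancers; physical examination and mammography remain even on the reduced list; and relapses found late still count.

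The conflict itself is not answered. Section 5.4.1 points to 7.3, not 7.2.2. Section 7.3 calls the Arm B visits therapy examinations, and if 7.2.2 already covered women off drug the Arm A sentence would be unnecessary. Serious adverse event reporting is no substitute: more than 30 days after the drug is stopped, an event is reportable only if a causal link cannot be excluded (9.3.2).

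**Conclusion.** The point holds as a conflict between passages that leaves open an arm-dependent route of ascertainment. It is not a stated rule of unequal follow-up. If sites follow 5.4.1 into 7.3, fracture survey and chest and abdominal imaging could be thinner for Arm B women off drug in years 2 to 5, tending to favour 5 years. If sites apply 7.2.2 to everyone, the effect is zero.

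The size cannot be computed from the documents. The DFS range of 1.005 to 1.14 under a true ratio of 1.00 rests on assumed f and m and describes years 2 to 5 only. The fracture comparison is the more exposed, because the survey is absent from the itemised 7.3 list and the SAP censoring visit is undefined for women off drug. This should be fixed because a wording change closes the route; confidence that it affected the data is no more than moderate.

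**What to change.** Reconcile 5.4.1 (5.5.1), amended 7.2.2, 7.2.3 and amended 7.3. State that outcome ascertainment to month 60, meaning the fracture survey and the relapse examinations, follows time since randomisation, is identical in both arms, and does not depend on whether or when anastrozole was stopped. Let the reduced annual list apply only after month 60, in both arms, and make the flow chart agree.

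In SAP 3.6.4, replace the last therapy visit with the last scheduled visit up to month 60 that has a fracture assessment, on or off drug, in both arms.

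The cost is amendment wording. The visits are already in the schedule; the one burden is keeping early stoppers on them.

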5.4.2. Discontinuation of the entire trial

The entire clinical trial may be interrupted or terminated at any time by the Coordinating Investigator in consultation with AstraZeneca due to considerations of risk vs. benefit where criteria leading to discontinuation in an individual case occur in an intolerably frequent manner or new knowledge regarding adverse effects or interactions of the study drug render this necessary.

AstraZeneca in agreement with the Coordinating Investigator reserves the right to discontinue the trial at any time, if

1. A change in the benefit vs. risk ratio precludes the continuation of the study for medical ethical reasons
2. The results of the planned interim analysis (see 10.3.) mean that it no longer appears to make sense to continue the study
3. There is a delay in patient recruitment (evaluation after enrolment of 2000 patients) and it can be assumed that the recruitment period will be extended by $\geq 25\%$.

5.4.3. Closure of an individual site

AstraZeneca, in agreement with the EC of the ABCSG, is entitled to close individual sites subject to the following conditions:

1. Lack of recruitment
2. Lack of cooperation of the site
3. Other reasons that speak against correct conduct of the study

6. STUDY DRUG

6.1. Information on anastrozole

Name of product:	Arimidex®
Name of the manufacturer:	AstraZeneca Pharmaceuticals
Composition:	Each film-coated tablet contains 1 mg anastrozole as the active substance
Pharmaceutical form:	Film-coated tablet
Shelf life:	5 years
Storage advice:	Store below 30°C
Pack size:	112 tablets

6.2. Labelling

The investigational product is labelled in accordance with Section 32 para. 7 of the Austrian AMG.

6.3. Provision of the study drug

Anastrozole (Arimidex®) is supplied to each patient free of charge in containers containing 112 tablets for the entire treatment period.

6.4. Dosage

1 mg film-coated tablet of anastrozole is taken once daily. The duration of therapy is 2 or 5 years.

6.5. Dose modifications and delays

There are no dose modifications for anastrozole. A temporary interruption of treatment is only permitted for a maximum of 3 months.

6.6. Handling of the study drug by the investigator and documentation of its whereabouts

AstraZeneca will supply the required quantity of the study drug for the clinical trial. The study drug must only be dispensed to patients in this protocol. The investigator will confirm correct receipt of the study drug in writing and ensure secure and appropriate storage.

Each pack comes with a tear-off, self-adhesive label. The investigator must fill in the dispensing date on the day of dispensing to the patient and stick it into the "Prescription Record Cards" in the CRF. Return of any medication must also be documented on an individual basis.

The monitor will examine full documentation of the whereabouts of the study drug during regular visits to the investigator and will resolve any discrepancies between used and dispensed study drug. The result is documented in the Monitoring Report.

A "Drug Accountability Log" is kept, in which receipt of the study drug, patient-specific study drug withdrawals and stock are recorded at monitoring visits.

6.7. Disposal of the study drug

Any trial drug that is returned by patients or unused (e.g. expired) is passed on to AstraZeneca by the Monitor to be destroyed.

